4.5. Study limitations

- The study participants who decide to enroll in this study are already aware whether they received RSVPreF3 or control. Study participants from prior RSV MAT pregnancy studies who experienced an adverse pregnancy outcome or a pregnancy/infant event from a prior pregnancy, may choose to participate in the current study at different rates than those who did not. This may lead to selection bias. As we have information on prior vaccination/control and prior adverse events/outcomes, we can evaluate whether this occurs and consider statistical analysis approaches to adjust for this.
- Comparison between incidence of events or outcomes in this study and events or outcomes in previous RSV MAT studies likely cannot be made directly because of the following possible limitations: 1) the expected sample size for this study is too small for the study to be adequately powered for comparisons, 2) this study has different inclusion and exclusion criteria, 3) this study has different timepoint of pregnancy at enrollment (as early as possible), and 4) different risk factors for participants in this study, such as a relatively short inter-pregnancy interval for pregnancies included in this study.
- This study includes two cohorts, one for which ***all*** data will be collected retrospectively and the other cohort for which data will be collected prospectively (***with some retrospective data collection***). This approach was taken so that the number of enrolled participants can be maximized. However, this may result in underestimation of the true incidence of AESIs in a pooled cohort (retrospective and prospective), as the retrospective cohort is more subject to recall bias.
- This study is conducted with a proportion of the same participants enrolled in previous RSV MAT studies which uncovered a safety signal, as described in Section 2.2. As there is still no plausible mode of action or known imbalance in risk factors across RSVPreF3 vs. control groups identified that explains the safety signal, the possibility remains there is unknown confounding (an unmeasured risk factor or exposure) leading to the safety signal. If there is unknown confounding, that may lead to a similar safety finding in this study.

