2	
Diagnosis of pregnancy established by any of the following criteria in the absence of Level 1 criteria:
 
 1. LMP date 2. Serial Symphysio Fundal Height examinations 
AND
 
Death of the mother while pregnant or within 42 days of termination of pregnancy, irrespective of the duration and site of the pregnancy And
 
Documentation of Cause of death as:
 
 3. Direct: abortive outcome, hypertensive disorder, obstetric hemorrhage, pregnancy related infection, other obstetric complications, unanticipated complications 4. Indirect: non-obstetric complications 5. Death during pregnancy, childbirth and the puerperium: other or coincidental 6. Unspecified: unknown or undetermined
3	
Absence of Level 1 or 2 criteria for establishing diagnosis of pregnancy and:
 
 1. Unsure LMP 2. No clinical examination documented 
AND
 
Death of the mother temporal to pregnancy, childbirth or the postpartum period when exact timing of death is unknown
 
AND
 
Documentation of cause of death as:
 
 3. Direct: abortive outcome, hypertensive disorder, obstetric hemorrhage, pregnancy related infection, other obstetric complications, unanticipated complications 4. Indirect: non-obstetric complications 5. Death during pregnancy, childbirth and the puerperium: other or coincidental 6. Unspecified: unknown or undetermined.

Reference [[Patwardhan, 2016](#)]: Patwardhan M, Eckert LO, Spiegel H, et al. Maternal death: Case definition and guidelines for data collection, analysis, and presentation of immunization safety data. Vaccine. 2016;34(49):6077-6083.

Table 16 Hypertensive disorders of pregnancy (Gestational hypertension, Pre-eclampsia, Pre-eclampsia with severe features including eclampsia)

Levels of Diagnostic Certainty (Highest level (1) to lowest level of certainty)	
Gestational Hypertension	
Level	Description
All	Clinical syndrome characterized by pregnancy ≥ 20 weeks AND New onset hypertension (systolic blood pressure ≥ 140 mmHg and/or diastolic blood pressure ≥ 90 mmHg) sustained on two measurements over a minimum of 1 h WITHOUT severe features (see preeclampsia with severe features category) and WITHOUT proteinuria
1	No proteinuria (as defined by 24 h urine collection < 300 mg, spot protein:creatinine ratio < 0.3)
2	No proteinuria (as defined by urine dipstick negative or trace)

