3. ANALYSIS SETS

Table 2 Maternal Participants

| Analysis Set | Definition / Criteria | Analyses Evaluated |
|-------------------------|---|---------------------------------------|
| Screened | All participants who were screened for eligibility. | Study Population |
| Enrolled | All maternal subjects who completed the informed consent process and signed the informed consent form and were determined eligible for study participation. Note screening failures (who never passed screening even if rescreened) are excluded from the Enrolled analysis set as they did not enter the study. | Study Population |
| Full Analysis Set (FAS) | All maternal subjects who had pregnancy defined by this study (defined in the Protocol Section 5.1). | Primary, Secondary and other analyses |

Table 3 Infant Participants

| Analysis Set | Definition / Criteria | Analyses Evaluated |
|-------------------------|--|---------------------------------------|
| Enrolled Infant | Infants live-born to the maternal set, whose parents/LARs completed the informed consent process and signed the informed consent form. | Study Population |
| Full Analysis Set (FAS) | All infant subjects in the infant set who have post-delivery/birth data. | Primary, Secondary and other analyses |

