4.2.1. Definition of primary endpoints

The first pregnancy during study period is defined as the first pregnancy conceived post-vaccination or control in participants enrolled in RSV MAT studies (those previously received RSVPreF3 or control) up to Day 42 post-delivery.

Pregnancy outcomes include (not limited to):

1. Live birth
2. Spontaneous abortion

3. Stillbirth
4. Elective/therapeutic termination
5. Live birth Congenital anomaly(ies)
6. Spontaneous abortion Congenital anomaly(ies)
7. Fetal death/still birth Congenital anomaly(ies)
8. Elective/therapeutic termination Congenital anomaly(ies)

| Pregnancy-related AESIs | Infant AESIs |
|---|--|
| 
 • Hypertensive disorders of pregnancy: 
 – gestational hypertension, – pre-eclampsia, – pre-eclampsia with severe features including eclampsia; • Fetal growth restriction; • Pathways to preterm birth: 
 – premature preterm rupture of membranes, – preterm labor, – insufficient cervix – provider-initiated preterm birth; • Gestational diabetes mellitus; and • Chorioamnionitis. | 
 • Small for gestational age, • Low birth weight including very low and extremely low birth weight (<2500 g, <1500 g, <1000 g), • Congenital anomalies: 
 – major external structural defects, – internal structural defects, – functional defects, • Neonatal death 
 – in a non-viable live birth [<22 weeks gestation] – in an extremely pre-term birth [22.GA<28 weeks], – in a preterm live birth [28.GA<37 weeks], – in a term live birth, • Preterm birth |

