4.2.2. Main analytical approach

All primary analyses will be performed on the Full Analysis Set.

Main primary analyses in maternal participants will include summaries of pregnancy outcomes and pregnancy related AESIs overall and by study arms. Pathways to preterm birth will be further broken down as: extremely preterm births (GA at birth: < 28 weeks); very preterm births (GA at birth: 28 - < 32 weeks); moderate to late preterm births (32 - < 37 weeks).

Main primary analyses in infant participants will include summaries overall, by study arms and by gestational age at birth (≥ 37 weeks or < 37 weeks; overall) of infant AESIs.

Primary endpoints will be reported by study arms while stratified by **CCI**

Pregnancy outcomes analytical approach:

The number and percentage of each pregnancy outcome is calculated among the maternal Full Analysis Set (for participants with medical records available), per pregnancy regardless of the number of fetuses in the concerned pregnancy.

The pregnancy related adverse events of special interest (AESIs) analytical approach:

The number and percentage of each pregnancy related adverse event of special interest is calculated based on the number of pregnancies reporting the symptom at least once. In addition, we will report the occurrence of pregnancy related adverse events of special interest. Only pregnancies based on medical record collection will be considered.

For infant participants, the infant participant reporting AESIs analytical approach:

The number and percentage of each neonatal adverse event of special interest is calculated based on the number of infants reporting the symptom at least once. In addition, we will report the occurrence of neonatal adverse events of special interest. Infants' data based on medical records only, will be considered.

CCI

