4.3.1.2. Main analytical approach

Refer to Section 4.2.2. All secondary analyses will be performed on the Full Analysis Set.

Main secondary analyses in maternal participants will include summaries of pregnancy outcomes and pregnancy related AESIs overall and by study arms. Pathways to preterm birth will be further broken down as: extremely preterm births (GA at birth: < 28 weeks); very preterm births (GA at birth: 28 - < 32 weeks); moderate to late preterm births (32 - < 37 weeks).

Main secondary analyses in infant participants will include summaries overall, by study arms and by gestational age at birth (≥ 37 weeks or < 37 weeks; overall) of infant AESIs.

Secondary endpoints will be reported by study arms while stratified by CCI

Pregnancy outcomes analytical approach:

The number and percentage of each pregnancy outcome is calculated among all pregnancies (for pregnancies with medical records available), per event regardless of the number of fetuses in the concerned pregnancy.

The pregnancy related adverse events of special interest (AESIs) analytical approach:

The number and percentage of each pregnancy related adverse event of special interest is calculated based on the number of pregnancies reporting the symptom at least once. In addition, we will report the occurrence of pregnancy related adverse events of special interest. Only pregnancies based on medical record collection will be considered.

For infant participants, the infant participant reporting AESIs analytical approach:

The number and percentage of each neonatal adverse event of special interest is calculated based on the number of infants reporting the symptom at least once. In addition, we will report the occurrence of neonatal adverse events of special interest. Infants' data based on medical records only, will be considered.

CCI

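### Hypertensive disorders and chorioamnionitis cannot occur before 20 and 22 0/7 weeks by definition, yet as the SAP reads their percentages include pregnancies that ended earlier

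*SAP*

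**What the plan says.** For pregnancy-related AESIs in the first pregnancy, SAP 4.2.2 counts pregnancies with the event: "The number and percentage of each pregnancy related adverse event of special interest is calculated based on the number of pregnancies reporting the symptom". SAP 4.3.1.2 repeats the rule for any study pregnancy and adds the only visible restriction, which SAP 4.2.2 also carries: "Only pregnancies based on medical record collection will be considered".

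The analysis set comes from two other statements. SAP 4.2.2: "All primary analyses will be performed on the Full Analysis Set". SAP Section 3, Table 2, defines that set for mothers as "All maternal subjects who had pregnancy defined by this study (defined in the Protocol Section 5.1"; no minimum gestation is attached. Early-ending pregnancies belong to it, since SAP 4.2.1 lists "Spontaneous abortion" and elective or therapeutic termination among the pregnancy outcomes.

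The case definitions are in Protocol Section 10.6. In Table 16, gestational hypertension and both pre-eclampsia categories open with "Clinical syndrome characterized by pregnancy", followed by a limit of 20 weeks or more. In Table 23, every level of chorioamnionitis requires 22 0/7 weeks or more.

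Protocol 4.5 notes that pregnancies are observed earlier here than in the parent studies: "this study has different timepoint of pregnancy at enrollment (as early as possible").

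**The concern.** The primary objective is the incidence of these events by study arm. A pregnancy that ended at 10 weeks can never be a case of pre-eclampsia or chorioamnionitis under the protocol's definitions, but it still adds one to the denominator. For these two groups the percentage therefore mixes the risk of the event with the frequency of early endings. If early endings are more common in one arm, that arm shows a lower AESI percentage for a reason unrelated to the AESI.

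The documents give reasons why early endings might be recorded unequally, even without a vaccine effect. Participants know their earlier allocation and may enrol selectively (Protocol 4.5). The retrospective cohort rests on a single contact and the prospective cohort on repeated contacts (Protocol 8.4.5.2 and 8.4.5.3). Retrospective entry is written in terms of a pregnancy that has reached Day 42 after delivery (Protocol 5.1.1), without saying how an early loss meets that. The same arithmetic therefore applies to the comparison of cohorts in SAP 4.6.2.3.

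**Working it through.** **The plan's own figures.** They reproduce and are not in question.
- At least one event among 100 pregnancies at a 5% rate: 1 − 0.95^100 = 99.4%, as stated.
- Clopper-Pearson 95% interval for 15/300: 2.8% to 8.1%, as stated.
- Participants with a pregnancy: 2540 × 0.10 × 0.60 + 5700 × 0.50 × 0.30 × 0.60 = 152 + 513 = 665, stated as about 650.

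**Which AESI groups have a gestational floor** (list in SAP 4.2.1, definitions in Protocol Section 10.6):

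| AESI group | Lower limit in its definition |
|---|---|
| Hypertensive disorders (Table 16) | 20 weeks |
| Chorioamnionitis (Table 23) | 22 0/7 weeks |
| Gestational diabetes (Table 20) | None as such; glucose tolerance tests mostly timed at 24–28 weeks, but Level 3 also accepts a fasting glucose with no timing |
| Fetal growth restriction (Table 19) | None stated |
| Pathways to preterm birth (Table 22) | Insufficient cervix: 16 to under 24 weeks; other pathways: only the upper limit of 37 weeks |

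Two of the five groups have a floor at 20–22 weeks.

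**Formulas.** Let p be the risk among pregnancies reaching the limit and L the share ending before it. No case can arise before the limit, so:
- percentage over all pregnancies = p × (1 − L);
- ratio over all pregnancies = ratio among those reaching the limit × (1 − L1)/(1 − L0), with 1 = RSVPreF3 and 0 = control.

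**Assumptions.** The documents give no early-ending share, no rate for these AESIs and no arm split. I take L from 10% to 30%, p = 10%, and 325 pregnancies per arm (half of about 650).

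**One group.** At p = 10%, the reported percentage is 9.0% (L = 10%), 8.0% (L = 20%) or 7.0% (L = 30%). Put the other way, the plan's 15/300 = 5.0% becomes 15/270 = 5.6% (95% CI 3.1 to 9.0) at L = 10%, and 15/240 = 6.3% (3.5 to 10.1) at L = 20%, when only continuing pregnancies are counted.

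**Two arms, same true risk:**

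| L1 (RSVPreF3) | L0 (control) | Reported ratio | True ratio that would read as 1.00 |
|---|---|---|---|
| 10% | 10% | 1.00 | 1.00 |
| 15% | 10% | 0.94 | 1.06 |
| 20% | 10% | 0.89 | 1.13 |
| 25% | 15% | 0.88 | 1.13 |
| 30% | 10% | 0.78 | 1.29 |

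For the 25% versus 15% row: 0.10 × 0.75 = 7.5% and 0.10 × 0.85 = 8.5%, ratio 0.88, about 12% below the true value of 1.00. A true ratio of 0.85/0.75 = 1.13 would be hidden.

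**Against sampling error.** In that row the expected events are 325 × 0.075 = 24.4 and 325 × 0.085 = 27.6. The standard error of the log ratio is √(0.925/24.4 + 0.915/27.6) = 0.267, so the Wald 95% interval is 0.88 × exp(±1.96 × 0.267) = 0.52 to 1.49.

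**With the added denominator.** 24.4/243.75 and 27.6/276.25 are both 10%, ratio 1.00.

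**The case against.** **The denominator is not written.** SAP 4.2.2 names its base for pregnancy outcomes but not for AESIs. A reader might say the SAP prescribes the wrong denominator; the text does not support that. The all-pregnancy base is an inference from the analysis set and the medical-record restriction. This stands, and it makes stating the denominator the first part of the fix.

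**Most AESIs are not affected in this way.** A reader might extend the point to every late-pregnancy event, with a 24-week base for gestational diabetes and a 20-week base for the preterm pathways. The case definitions do not support that. Gestational diabetes has an untimed fasting-glucose route. Insufficient cervix can occur from 16 weeks, so a 20-week base would leave some cases in the numerator without their pregnancies in the denominator. This stands and limits the point to two groups.

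**Early losses are already shown.** Spontaneous abortion and termination are primary outcomes tabulated by arm, so an imbalance would be visible. SAP 4.6.2.3 responds to a cohort difference with further assessment, not a conclusion. The primary analysis is descriptive; relative risks with p-values appear only in the risk-factor analysis (SAP 4.3.2.2). This largely stands. However, those tables do not give the share ending before 20 or 22 weeks, so a reader could not correct the AESI percentage from them.

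**Incidence per pregnancy is a legitimate quantity,** and the alternative conditions on an event after exposure. This stands, so the existing figure should stay.

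**Redaction.** SAP 4.2.3 on sensitivity analyses is not visible and may address this. That cannot be excluded, but the main rule is visible and carries no gestational limit.

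**Conclusion.** The point holds for hypertensive disorders and chorioamnionitis. On the natural reading of the SAP, both percentages are diluted by the share of pregnancies that ended before 20 or 22 0/7 weeks, and an arm or cohort ratio is multiplied by (1 − L1)/(1 − L0). With equal early endings the ratio does not move.

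The size is modest. An assumed 25% versus 15% in early endings shifts the ratio by about 12%, against an interval of about 0.52 to 1.49 at an assumed 325 per arm. The shift is systematic and the interval does not reflect it, but it would rarely decide a conclusion on its own. A reader might infer that the RSVPreF3 arm will look safer than it is. The documents do not support that, because they give no early-ending rates by arm and no direction for any difference.

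This is an improvement to consider, not a defect that undermines the primary analysis.

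**What to change.** In SAP 4.2.2 and 4.3.1.2:
1. State the denominator for pregnancy-related AESIs.
2. Keep the percentage over all pregnancies.
3. Add a supplementary percentage by arm, with its exact interval, among pregnancies that reached 20 weeks (hypertensive disorders) and 22 0/7 weeks (chorioamnionitis).
4. Show beside it the number of pregnancies that ended before each limit, by arm. Use the same layout where SAP 4.6.2.3 splits by cohort.

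Add no gestational cut-off for gestational diabetes, fetal growth restriction or the pathways to preterm birth.

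Use gestational age at the end of pregnancy as recorded. Where it is recorded only for births, derive it from the conception date, which SAP 6.2.2 already uses as the safety reference date, and state the conversion to gestational weeks.

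The cost is a few sentences and extra columns in two sets of tables; no new data collection appears necessary if the conception date and the date the pregnancy ended are held. The downside is that the added figure conditions on the pregnancy surviving to the limit, which is why it should stand beside the all-pregnancy figure and not replace it.

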8.3.1. Safety monitoring and committee

Safety evaluations will include those performed by investigators, as well as those by a SRT composed of GSK RSV team members.

A SRT is in place for each GSK product. It comprises of a global cross-functional team responsible for the ongoing assessment of benefit-risk for a product. The SRT contribute to the continual assessment of incoming new efficacy and safety information.

If the SRT's decision(s) after a safety evaluation require(s) them to take some action (e.g., to suspend, modify, or continue the conduct of the study for all groups or for selected groups), the SRT Chair (or his/her representative) will notify the study **CSL**. The study **CSL** will be accountable for notifying investigators in writing of the SRT's decision(s).

An external case adjudication committee will provide an independent, objective, blinded review and judgement on cases of preterm births. The scope of review by this committee will be limited to only review of gestational age at birth (to determine status of preterm birth cases) and preterm birth cases but may be expanded at the discretion of the GSK clinical study team. The details of structure and scope of this committee will be included in external case adjudication committee charter.

8.4. MAEs, serious adverse events (SAEs) and SAEs due to study participation, AESIs, and other safety reporting

For definitions relating to safety information see Section 10.2.

The investigator and any qualified designees are responsible for detecting, documenting, and recording events that meet the definition of a MAE, SAEs, AESI (see Section 10.2), SAE due to study participation and other safety information and remain responsible for following up all MAEs, SAEs, AESIs, SAEs considered related to the study participation that caused the participant to discontinue the study (see Section 7). This includes events reported by the participant (or, when appropriate, by a caregiver, surrogate, or the participant's legally authorized representative).

SAEs due to study participation, defined as SAEs which in the opinion of the investigator are related to the study participation (e.g., accident during any of the study contact and/or **study** visit) will be recorded throughout the study period.

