8.4.5.2. Retrospective data source and data collection

For *pregnancies completed (through Day 42 post-delivery) prior to enrollment*, medical data related to pregnancy outcome, pregnancy related AESIs and infant AESIs of any pregnancy conceived post-RSVPreF3 or control vaccination, based on medical records, will be retrospectively collected. ***Data collection will be done through a single structured participant contact to retrospectively collect information about any healthcare received by the mother and infant during pregnancy up to Day 42 post-delivery. This will identify the medical records for review, so that information about any outcome, medically attended event, SAE, or event of special interest is obtained directly from medical records.***

All relevant data collected in the medical records will be recorded in an electronic case report form (eCRF).

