System	Score																																																																																			
	0	1	2	3	4																																																																															
Respiration																																																																																				
Pao ₂ /Fio ₂ , mm Hg (kPa)	≥400 (53.3)	<400 (53.3)	<300 (40)	<200 (26.7) with respiratory support	<100 (13.3) with respiratory support																																																																															
Coagulation																																																																																				
Platelets, ×10 ³ /μL	≥150	<150	<100	<50	<20																																																																															
Liver																																																																																				
Bilirubin, mg/dL (μmol/L)	<1.2 (20)	1.2-1.9 (20-32)	2.0-5.9 (33-101)	6.0-11.9 (102-204)	>12.0 (204)																																																																															
Cardiovascular	MAP ≥70 mm Hg	MAP <70 mm Hg	Dopamine <5 or dobutamine (any dose) ^b	Dopamine 5.1-15 or epinephrine ≤0.1 or norepinephrine ≤0.1 ^b	Dopamine >15 or epinephrine >0.1 or norepinephrine >0.1 ^b																																																																															
Central nervous system																																																																																				
Glasgow Coma Scale score ^c	15	13-14	10-12	6-9	<6																																																																															
Renal																																																																																				
Creatinine, mg/dL (μmol/L)	<1.2 (110)	1.2-1.9 (110-170)	2.0-3.4 (171-299)	3.5-4.9 (300-440)	>5.0 (440)																																																																															
Urine output, mL/d				<500	<200																																																																															

References [Ko, 2006; Geenes, 2016; Bonet, 2017]:

¹ Geenes V. Williamson C, Chappell L. Intrahepatic cholestasis of pregnancy. The Obstetrician and Gynecologist. 2016; 18:273-81.

² Ko H, Yoshida E. Acute Fatty Liver of Pregnancy. Can J Gastroenterol. 2006; 20:25-30.

³ Bonet M, Pileggi V, Rijken M et al. Towards a consensus definition of maternal sepsis: results of a systematic review and expert consultation. Reproductive Health. 2017; 14:67.

Table 25 Small for Gestational Age

Weight below 10th percentile for gestational age as assessed against a validated global, regional or local standard.

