6.2.4.4. Weight

Weight will be presented in kilograms. Weights reported in pounds will be converted as follows:

Weight in kilograms = Weight in pounds / 2.2

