6.3.2. Summary Table and Listing

| Table # | Table Title |
|-----------|---|
| Table 1 | Summary of demography and baseline characteristics - Maternal participants |
| Table 2 | Summary of demography and baseline characteristics - Infant participants |
| Table 3 | Number and percentage of infants with birth weight below the 3rd and 10th percentile, as per the IG-21 standards - Infant participants |
| Listing 4 | Listing of infants with birth weight below the 3rd and 10th percentile, as per the IG-21 standards - Infant participants |
| Table 5 | Number and percentage of infants with birth weight below the 3rd and 10th percentile, as per the IG-21 standards - Pre-term subgroup < 37 weeks - Infant participants |
| Listing 6 | Listing of infants with birth weight below the 3rd and 10th percentile, as per the IG-21 standards - Pre-term subgroup < 37 weeks - Infant participants |

| Table # | Table Title |
|----------------|---|
| Table 7 | Number and percentage of infants with birth head circumference below the 3rd and 10th percentile, as per the IG-21 standards - Infant participants |
| Listing 8 | Listing of infants with birth head circumference below the 3rd and 10th percentile, as per the IG-21 standards - Infant participants |
| Table 9 | Number and percentage of infants with birth head circumference below the 3rd and 10th percentile - Pre-term subgroup < 37 weeks, as per the IG-21 standards - Infant participants |
| Listing 10 | Listing of infants with birth head circumference below the 3rd and 10th percentile, as per the IG-21 standards - Pre-term subgroup < 37 weeks - Infant participants |
| Table 11 | Summary of study completion with reasons for withdrawal - Maternal participants |
| Table 12 | Summary of study completion with reasons for withdrawal - Infant participants |
| Table 13 | Summary of medically attended adverse events - Maternal subjects |
| Table 14 | Summary of SAE - Maternal subjects |
| Table 15 | Summary of AESI - Maternal subjects |
| Table 16 | Summary of medically attended adverse events - Infant subjects |
| Table 17 | Summary of non-medically attended adverse events - Infant subjects |
| Table 18 | Summary of SAE - Infant subjects |
| Table 19 | Summary of AESI - Infant subjects |
| Table 20 | Summary of participants with at least one grade 3 adverse event - Maternal participants |
| Table 21 | Summary of participants with at least one grade 3 adverse event - Maternal pregnancies |

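### The SAP's pound-to-kilogram rule is wrong at the 2500 g cut-off, and its visible counting rule gives no role to adjudicated gestational age or measured birth weight

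*SAP*

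**What the plan says.** **Counting rule.** SAP 4.2.2 (primary) and 4.3.1.2 (any pregnancy) give the number and percentage for each infant AESI as "calculated based on the number of infants reporting the symptom at least once". The same paragraph restricts the source: infants' "data based on medical records only, will be considered". Protocol 8.4.5.2 agrees that any "event of special interest is obtained directly from medical records". The infant AESIs include preterm birth, LBW (below 2500, 1500 and 1000 g) and SGA.

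**Adjudication.** Protocol 8.3.1 states: "An external case adjudication committee will provide an independent, objective, blinded review and judgement on cases of preterm births". Its scope is gestational age at birth and preterm birth cases, with details left to a charter. The visible SAP does not mention the committee.

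**SGA standard.** Protocol Appendix 6, Table 25 defines SGA as "Weight below 10th percentile for gestational age as assessed against a validated global, regional or local standard". The SAP names one standard in its outputs for the safety review team (6.3.2, Table 3): "Number and percentage of infants with birth weight below the 3rd and 10th percentile, as per the IG-21 standards - Infant participants". Table 5 repeats this for preterm infants.

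**Conversion.** SAP 6.2.4.4: "Weight in kilograms = Weight in pounds / 2.2". SAP 6.2.5.4 has a display rule for transformed weights below 10 kg, so converted infant weights are expected.

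**Blinding.** The study is open label. Protocol 4.5: "The study participants who decide to enroll in this study are already aware whether they received RSVPreF3 or control".

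**The concern.** Preterm birth is the signal that led to this study, and incidence by arm is its main product. Three features of the plan bear on how well that incidence is measured.

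(a) The conversion factor is inexact, and its error falls on a cut-off the study uses. It always makes infants look heavier, so any misclassification hides small infants.

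(b) The protocol provides blinded review of gestational age, but the visible SAP does not say whether the committee's status or the site's enters the preterm endpoint and the split at 37 weeks. In an open-label study, blinded review protects the endpoint only if the analysis uses it.

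(c) LBW follows from a recorded weight. SGA follows from weight, sex and gestational age, all of which SAP 6.1.2 summarises. Yet both are counted as reported events, and SGA may rest on different standards in different countries. The primary SGA rate could then disagree with the sponsor's own IG-21 table, and no visible rule reconciles them.

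**Working it through.** The documents give no figure for reported against adjudicated or derived events. The nearest stated figure, a 99.4% chance of at least one event among 100 RSVPreF3 participants at a true rate of 5%, reproduces (1 - 0.95^100 = 0.99408) but does not bear on this point.

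**Conversion error.** One pound is 0.45359237 kg.
- Relative error: (1/2.2)/0.45359237 - 1 = +0.21%, for every weight.
- 5 lb 8 oz by the SAP rule: 5.5/2.2 = 2.5000 kg, which is not below 2500 g.
- 5 lb 8 oz exactly: 5.5 x 453.59237 = 2494.8 g, which is LBW.
- The 2500 g boundary lies at 5.500 lb under the SAP rule and at 2500/453.59237 = 5.5116 lb exactly.
- Of all whole-ounce weights up to 7 lb 15 oz, 5 lb 8 oz is the only one that changes category at 2500, 1500 or 1000 g. With decimal pounds to two places, 2.20, 3.30, 5.50 and 5.51 lb also change.
- BMI: 30 x 0.0021 = 0.06 units at the subgroup boundary of 30.

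**How many infants.** Assumptions, not in the documents: birth weight is normal with mean 3200-3400 g and SD 450-550 g, and is recorded to the nearest ounce. One ounce is 28.35 g, so infants recorded as 5 lb 8 oz truly weigh 2480.6 to 2508.9 g. Write F for the cumulative distribution.

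Central case, mean 3300 g and SD 500 g: F(2480.6) = 0.05062, F(2500) = 0.05480, F(2508.9) = 0.05681.
- Share of births in the bin: 0.05681 - 0.05062 = 0.62%.
- Share of those recorded as LBW under exact conversion: 0.0062/0.0568 = 10.9%.
- Net undercount of true LBW under the SAP rule: (0.05480 - 0.05062)/0.05480 = 7.6%.

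| Quantity | Range over the assumed means and SDs |
|---|---|
| Births in the 5 lb 8 oz bin | 0.3-0.9% |
| Bin as share of recorded LBW | 9-14% |
| Net undercount of true LBW | 6-10% |

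The last two rows differ because about 32% of the bin truly weighs 2500 g or more. If all 650 expected pregnancies gave one infant weighed in ounces, the bin would hold 650 x 0.0033 to 650 x 0.0090, or about 2 to 6 infants.

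**Where the rule acts.** If LBW is counted from reported AESIs, as SAP 4.2.2 reads, the conversion does not enter that count. It acts on anything derived from converted weight: the IG-21 tables, BMI, and a derived LBW variable if one is added.

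**Adjudication.** Protocol 8.3.1 has the committee determine preterm status. SAP 4.2.2 and 4.3.1.2 count reports and split infants at 37 weeks without naming the source of gestational age. SAP 4.2.3 is blacked out. The visible text is therefore silent on adjudication; it does not reject it.

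**SGA.** Table 25 admits any validated standard, and its lowest certainty level includes infants noted as small with no recorded weight. The visible SAP sets no minimum certainty level for counting.

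**The case against.** A reader might infer that the SAP deliberately bypasses blinded adjudication. The documents do not support that: nothing visible excludes it, 4.2.3 is redacted, and the charter is not public. It would also be wrong to extend the adjudication argument to LBW and SGA, which are outside the committee's stated scope unless that is expanded.

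A reader might also infer that the endpoints rest on participants' or sites' opinion. They do not. Events come from medical records under GAIA definitions, and the counting phrase is not evidence of self-report. The statement in Protocol 4.5 about known allocation is made there about selection into the study. A participant's knowledge of her arm does not alter a charted birth weight. Bias in site abstraction remains possible, but the documents give no means of sizing it.

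Nor does the conversion rule by itself remove infants from the planned LBW count, for the reason given above. The study is multi-country, the share weighed in pounds is unknown, and the same factor applies to both arms.

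Finally, SAP 4.5 describes the safety review team's material as including a subset of the analysis outputs, so the IG-21 tables may also appear elsewhere. Naming IG-21 for the SGA endpoint is then partly harmonisation.

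These points limit the size of the concern. They do not make division by 2.2 correct, and they do not tell a programmer which preterm status to analyse.

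**Conclusion.** (a) SAP 6.2.4.4 is wrong as written and should be corrected. The effect is 0.21% on each converted weight and a changed category at 5 lb 8 oz wherever LBW is derived from it. The estimates of 0.3-0.9% of births, 9-14% of recorded LBW and a net 6-10% of true LBW apply only to infants weighed in pounds and ounces, and rest on the assumed birth-weight distribution. The effects on the IG-21 tables and on BMI are slight.

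(b) and (c) are inexpensive improvements. For preterm birth, the visible SAP leaves open which status is analysed. For LBW and SGA, recorded data and a planned single-standard output exist, but the visible primary rule does not use them. Neither can be given a numerical size from the documents.

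**What to change.** - **SAP 6.2.4.4:** kilograms = pounds x 0.45359237, with ounces included as sixteenths of a pound, or use grams as recorded. Grams are preferable where available. Exact conversion cannot undo rounding to the ounce: in the central case above it would overcount true LBW by (0.05681 - 0.05480)/0.05480 = 3.7%.
- **SAP 4.2.2 and 4.3.1.2, preterm birth:** define preterm birth and the split at 37 weeks by adjudicated gestational age (below 259 days, as in Protocol Table 33) where available, and by recorded gestational age otherwise. The fallback is needed because the committee may not review every infant. Report site-reported AESIs as a sensitivity analysis.
- **SAP 4.2.2 and 4.3.1.2, LBW and SGA:** derive the three LBW categories from recorded weight, and SGA from weight, sex and gestational age with IG-21, for every infant with these data. List discordances with the reported AESIs.

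The cost is SAP wording and programming. The committee and the IG-21 outputs are already planned, and no new data are needed. The downside is that derived counts may differ from reported AESIs, so a reconciliation listing must be produced and explained.
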